## 5.4.2 Instructions for Use – Study Drugs and Non-Investigational Products

Table 3: Guidelines for Using Study Drugs and Non-Investigational Products

[figure not shown]
	Trifarotene Cream				
	OR				
Trifarotene Vehicle Cream					
Study Drug Usage	
 
Apply a thin layer to the face once daily, in the evening. The face should be washed and patted dry, before use.
 
One pump actuation should be enough to cover the face (i.e., forehead, cheeks, nose, and chin).
 
				
	The Investigator may instruct alternate day regimen application of the topical study drug (detailed subject instruction will be provided) and re-evaluate at each visit to modify accordingly following the Baseline visit. Refer to Section 5.4.8 – Dose Modification of Topical Study Drug.				
	Non-Investigational Product Use Guidelines *				
Cetaphil® Gentle Skin C	Cleanser: Topical, wash face, twice daily, in the morning and evening.				
Cetaphil® Dermacontrol day, reapply every two h	Moisturizer SPF 30: Topical, apply after morning cleansing. If sun exposure during the nours.				
Cetaphil® Moisturizing Lotion: Topical, if extra moisture is needed, apply as needed.					
Duration of administrati	on for the above products: 24 weeks				

\* These are guidelines for non-investigational product use and will not be recorded as protocol deviations. Subjects will be counselled on the importance of using non-investigational products per the study guidelines, throughout the study. Compliance and protocol deviation reporting will apply only to study drug products. Alternative cleanser and moisturizers are not permitted, only the supplied non-investigational products to be used.

# **5.4.3** Topical Study Medication Application

The subject will apply the topical study drug on the face once a day (evenings): chin, left cheek, right cheek, nose and forehead (avoiding application in/close to eyes, angles of the mouth, lips and mucous membranes).

GALDERMA R&D RD.06.SPR.204245 V00 18AUG2021 Page 41 of 104

Avoid application in/close to eyes, or angles of the mouth, lips and mucous membrane.

The objective is to cover the face with a thin layer of the study drug, even on areas on the face with no clinically evident acne (no spot or localized treatment). One pump actuation should be enough to cover the forehead, right cheek, left cheek, nose, and chin. Avoid application in/close to eyes, or angles of the mouth, lips and mucous membrane.

The study drug should not be applied to cuts, abrasions, eczematous, or sunburned skin.

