A major concern with the use of topical retinoids in skin of color includes the potential for inducing a retinoid dermatitis, which is characterized by xerosis, peeling, and erythema of the skin (Taylor 2009). There are several ways to mitigate this adverse effect and prevent further worsening of acne-induced pigmentation. These include initiating patients on lower concentrations of topical retinoids, or choosing cream or lotion (over gel). Trifarotene, being a selective RAR-x agonist with low concentration and in cream formulation would be appropriate for use in PIH acne. Also, the addition of a topical gentle moisturizer (Davis 2010, Yin 2014, and Taylor 2009) and avoiding sun exposure is recommended as part of the skin care regimen in acne patients. Minimizing skin irritation and photoprotection can be achieved by the use of noncomedogenic moisturizers with appropriate SPF that hydrate and protect the skin from UV irradiation (Schorr 2012, Del Rosso 2013, and Zeichner, 2011). As exposure to UV radiation is known to contribute to pigment disorders including PIH, solar protection is a key element in its management (Khemis 2007).

GALDERMA R&D RD.06.SPR.204245 V00 18AUG2021 Page 23 of 104

To ensure reliability of the efficacy assessments, patients will be instructed to avoid sun exposure during the course of the study and to use at least twice-daily a broad-spectrum sunscreen (SPF 30+). Moisturizing cream will also be provided for daily use to limit irritation. Also, using an appropriate cleanser will reduce oil on the face and will not affect skin hydration or the skin barrier function.

Acne can persist for years and may seriously affect psychosocial development, resulting in emotional problems, withdrawal from society, and depression (Koo 1991). If not treated, acne may cause serious physical and emotional scarring and can significantly impact the quality of life of those affected by the disease (Usatine 1998). Therefore, this study aims to evaluate efficacy of Trifarotene in acne lesions and Acne-induced hyperpigmentation in all skin phototype subjects. The local tolerance of the treatment regimen in terms of erythema, scaling, dryness, stinging/burning will also be evaluated.

This double-blind, randomized, vehicle-controlled clinical trial is the first to evaluate the clinical potential of trifarotene in treating Acne-induced hyperpigmentation in patients with acne.

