#### - DOSAGE AND ADMINISTRATION -

- · For topical use only. Not for oral, ophthalmic or intravaginal use.
- · Apply a thin layer of AKLIEF Cream to the affected areas of the face and/or trunk once a day, in the evening, on clean and dry skin. Avoid contact with the eyes, lips, paranasal creases, and mucous membranes. (2)

DOSAGE FORMS AND STRENGTHS — Cream: 0.005% trifarotene. (3)

----- CONTRAINDICATIONS -----None (4)

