## DOSAGE AND ADMINISTRATION

Apply a thin layer of AKLIEF Cream to the affected areas once daily, in the evening, on clean and dry skin.

- One pump actuation should be enough to cover the face (i.e., forehead, cheeks, nose, and chin).
- Two actuations of the pump should be enough to cover the upper trunk (i.e., reachable upper back, shoulders and chest). One
  additional pump actuation may be used for middle and lower back if acne is present.

The use of a moisturizer is recommended as frequently as needed from the initiation of treatment.

Avoid contact with the eyes, lips, paranasal creases, mucous membranes.

AKLIEF Cream is for topical use only. Not for oral, ophthalmic, or intravaginal use.

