Skin irritation was evaluated by active assessment of erythema, scaling, dryness, and stinging/burning and collected separately. In the two 12-week Phase 3 clinical trials, these signs/symptoms were assessed at baseline and at least one post-baseline visit, in 1214 subjects (for face) and 1202 subjects (for trunk) treated with AKLIEF Cream. The percentage of subjects who were assessed to have these signs and symptoms at any post baseline visit and at a severity worse than baseline are summarized in Table 2.

Table 2. Application Site	Tolerability	Reactions at Any	Post Baseline Visit
---------------------------	--------------	------------------	---------------------

Face	AKLIEF N=1214 Maximum Severity during Treatment			Vehicle Cream N= 1194 Maximum Severity during Treatment		
	Mild	Moderate	Severe	Mild	Moderate	Severe
Erythema	30.6%	28.4%	6.2%	21%	6.8%	0.8%
Scaling	37.5%	27.1%	4.9%	23.7%	5.9%	0.3%
Dryness	39%	29.7%	4.8%	29.9%	6.8%	0.8%
Stinging/Burning	35.6%	20.6%	5.9%	15.9%	3.8%	0.5%
Trunk		N=1202			N=1185	
Erythema	26.5%	18.9%	5.2%	12.7%	4.4%	0.4%
Scaling	29.7%	13.7%	1.7%	13.2%	2.6%	0.1%
Dryness	32.9%	16.1%	1.8%	17.8%	3.9%	0.1%
Stinging/Burning	26.1%	10.9%	4.3%	9.2%	2.2%	0.5%

Local tolerability on the face in subjects treated with AKLIEF Cream worsened for any of the signs/symptoms compared with baseline to a score of moderate for up to 30% of subjects, or severe for up to 6% of subjects. On the trunk, the corresponding percentages were up to 19% (moderate) and up to 5% (severe). The scores reached maximum severity at Week 1 for the face, and at Week 2 to 4 of treatment for the trunk, and decreased thereafter.

In the open-label, 1-year Phase 3 trial, the local tolerability profile was comparable to that observed in the two pivotal Phase 3 trials.

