## 17 PATIENT COUNSELING INFORMATION

See FDA-approved patient labeling (Patient Information).

Advise the patient to:

- Cleanse the area to be treated; pat dry. Apply AKLIEF Cream as a thin layer once daily in the evening to the face, avoiding the
  eyes, lips, nasolabial folds, and mucous membranes. A thin layer of AKLIEF Cream may also be applied to the chest, shoulders,
  and back.
- Avoid applying AKLIEF Cream to damaged skin (such as cuts, abrasions), eczematous areas, and sunburned skin.
- Reduce the risk of such irritation, use a moisturizer from the start of treatment, and, if appropriate, reduce the frequency of application of AKLIEF Cream or suspend use temporarily. AKLIEF Cream may cause irritation such as erythema, scaling, dryness, and stinging or burning.
- Minimize exposure to sunlight, including sunlamps and phototherapy devices.
- Use sunscreen products and protective apparel (e.g., hat) over treated areas when exposure to sunlight cannot be avoided.
- Avoid concomitant use of other potentially irritating topical products (medicated or not).
- Use AKLIEF Cream on the smallest area of skin and for the shortest duration possible while breastfeeding. Advise breastfeeding
  women not to apply AKLIEF Cream directly to the nipple and areola to avoid direct infant exposure.

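### The application instruction in Protocol 5.4.3 omits the paranasal creases and nasolabial folds, which the appended label says to avoid

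*Protocol*

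**What the plan says.** Protocol 5.4.3 is the section that tells the subject where to put the cream. It names chin, both cheeks, nose and forehead, and asks for coverage "even on areas on the face with no clinically evident acne (no spot or localized treatment". It limits this by "avoiding application in/close to eyes, angles of the mouth, lips and mucous membranes" and then prints the same four-item list twice more as a separate sentence. It also keeps the cream off cut, abraded, eczematous or sunburned skin.

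The label is reproduced as Appendix 14.9. Its Highlights say: "Avoid contact with the eyes, lips, paranasal creases, and mucous membranes". Its full Dosage and Administration section says: "Avoid contact with the eyes, lips, paranasal creases, mucous membranes". Its section 17, Patient Counseling Information, gives the areas as "eyes, lips, nasolabial folds, and mucous membranes".

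The study drug row of Table 3 in 5.4.2 reads: "Apply a thin layer to the face once daily, in the evening. The face should be washed and patted dry, before use". Its remaining text covers pump quantity and alternate-day use. As far as the published text shows, it has no list of areas to avoid.

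**The concern.** The protocol keeps the label's direction to cover nose and cheeks but drops one of the limits that goes with it. The skin beside the nose then falls inside an instruction to cover the whole face, acne or not. No rationale for departing from the label is given.

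What is at stake is local tolerability. Section 3.1 says: "A major concern with the use of topical retinoids in skin of color includes the potential for inducing a retinoid dermatitis". It goes on to discuss ways of mitigating this so that pigmentation does not worsen. Section 5.3.1 targets about 70% of subjects with Fitzpatrick types IV-VI, and the primary endpoint in 4.2.1 is a pigmentation score. In such a trial there is good reason to carry every label application precaution into the subject's instruction, or to explain its absence.

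**Working it through.** There is no figure to recompute. The check is a comparison of the lists.

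| Area to avoid | 5.4.3 (three statements) | Label Highlights | Label Dosage and Administration | Label section 17 |
|---|---|---|---|---|
| Eyes | yes | yes | yes | yes |
| Lips | yes | yes | yes | yes |
| Mucous membranes | yes | yes | yes | yes |
| Angles of the mouth | yes | no | no | no |
| Paranasal creases | no | yes | yes | no |
| Nasolabial folds | no | no | no | yes |

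1. *Count.* None of the 3 statements in 5.4.3 names either area. All 3 label statements name one of them: the paranasal creases twice and the nasolabial folds once. The label never lists both together.

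2. *Is the gap filled elsewhere?* The usage text in the synopsis gives quantity, timing and washing, but no areas to avoid. Table 3 is the same. Section 5.4.4 covers sun exposure, cosmetics, shaving and makeup removal, and does not mention the creases. In the protocol text provided, neither term appears outside Appendix 14.9.

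3. *Does the coverage instruction reach these areas?* Section 5.4.3 names both the nose and the cheeks, rules out localized treatment and includes acne-free skin. Read literally, this takes in the creases between nose and cheek. Covering nose and cheeks is itself the label's direction, so only the missing exceptions are at issue.

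4. *Does it look deliberate?* The protocol carries over the label's pump-quantity guidance, its caution about damaged skin (5.4.3) and its advice against waxing (Table 4). The avoid list departs from the label without comment, which suggests an oversight, though the documents do not settle it.

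**The case against.** Several points on the other side are sound.

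- *The label is in the protocol.* Investigators hold it as Appendix 14.9, and site staff instruct and counsel the subjects. This stands, and it means the omission from 5.4.3 is certain while what subjects were actually told is not. Any subject instruction sheet and the EU product information for the German and Spanish sites are not among the documents. The reliance is imperfect, though: 5.4.3 is the operative instruction, and section 3.4 cites the label as Appendix 14.8, which is the patch-test letter.

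- *The label ties no specific harm to the creases.* Its skin irritation warning (5.1) does not mention them. They appear only in the administration and counseling text, without a reason. This stands, so the link from the omission to extra irritation is an inference.

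- *The protocol list is not simply weaker.* It adds the angles of the mouth and covers application close to the listed areas as well as on them. The label says to avoid contact and lists no contraindications. This stands, but it does not supply the two missing areas.

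- *Safeguards exist.* Tolerability is checked at every post-Baseline visit (5.1.1.2), moisturizers are supplied (5.4.11), and 5.4.8 allows reduced frequency in the first 4 weeks for at most 2 weeks. These limit the risk. They would not show where irritation arose, because 6.3.5 records one global facial rating per sign.

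A reader might also try to size the problem from the label's facial tolerability results, where worsening on the active cream was "moderate for up to 30% of subjects, or severe for up to 6% of subjects". The documents do not support that use. Those are whole-face results, not results for the creases, and they would be the same if 5.4.3 matched the label exactly. They show that the cream irritates facial skin and say nothing about the omission.

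**Conclusion.** The point holds as a minor matter of label consistency and local tolerability. An application rule in the protocol differs, without explanation, from the label appended to the same protocol, and following the rule as written puts cream where the label says not to. The added irritation cannot be derived from the documents, so no size is given for it.

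Two stronger readings are not supported. A reader might infer a breach of the statement in 5.2 that the product is used according to its labeling; that statement is limited in parentheses to indication, population and dose regimen, so the gap is an inconsistency with the label's administration text and not a breach of that sentence. A reader might also infer a bias in the primary comparison. Both arms receive the same instruction, and nothing in the documents shows an effect on the Week 24 severity score; sample size and error rate are untouched. If the active cream did irritate the creases more than vehicle, that would be a consequence of the treatment as instructed, not a distortion of the randomized comparison.

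The conclusion rests on a literal reading of 5.4.3 and on the assumption that no subject material outside the documents already names the two areas. If such material does, the point reduces to a drafting correction.

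**What to change.** State the avoid list once in 5.4.3, replacing the three repeats, and add the paranasal creases and nasolabial folds. Keep the angles of the mouth. Put the same list in the study drug row of Table 3 (5.4.2) and in any subject instruction sheet. Naming both areas combines terms that the label uses in different sections, but it covers each of them. If the omission was intended, a sentence of rationale in 5.4.3 would serve instead.

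No visit, procedure or data item is added. The cost is more than the text edit: this changes an instruction to subjects, so under 8.4 and 8.5 it should be planned as a small protocol amendment with sponsor and IRB/IEC approval, followed by a short re-instruction of sites and enrolled subjects. It could reasonably be held for the next amendment made for other reasons, with sites reminded of the appended label in the meantime.

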## 5.4.4 Other Subject Instructions

The subject should maintain a consistent lifestyle throughout the study regarding exposure to external factors that may produce an exacerbation of their acne. These factors include, but are not limited to, excessive exposure to UV radiation (occupational exposure to the sun, sunbathing, tanning salon use, phototherapy, etc.). Subjects should avoid excessive sun exposure, wind and cold, as much as possible during the study. The subject will be instructed to apply the Cetaphil® Dermacontrol Moisturizer with SPF30 on the face every morning, and re-apply to the face and other exposed skin when sun exposure is expected. Subject should use protective apparel (e.g, hat) when sun exposure cannot be avoided. Avoid sunless tanning products for the duration of the study. Extra care should be taken to wear protective clothing and sunglasses and avoid sun exposure from 10 AM to 3 PM.

Cosmetics may generally be used during the study, but not on study visit days (or must be removed at least 30 minutes prior to study visit). Non-comedogenic cosmetics (cosmetics that do not cause acne) may be used as well as eye and lip makeup. Cosmetics can be applied after the study drug has dried. Foundation make-up is allowed on the days of study visits as long as subjects wash their face at least 30 minutes prior to the study visit. Use of moisturizing foundation will be acceptable during the study if subject has a history of safe usage of the foundation.

GALDERMA R&D RD.06.SPR.204245 V00 18AUG2021 Page 42 of 104

Topical study drug should be applied approximately 1 hour before or 1 hour after application of any other permitted skin care products (e.g. cosmetic products).

Products containing alcohol, alpha hydroxy or glycolic acids and astringents should not be used during the study.

Face shaving is allowed during the study. Male subjects with excessive facial hair that would interfere with acne assessments, as judged by the investigator, are not eligible to participate in the study. Male subjects with facial hair will be expected to keep areas well-groomed prior to study visits, as judged appropriate by the investigator, to perform the acne assessments.

Subjects should wash their face and remove all makeup at least 30 minutes prior to each scheduled clinic visit and should not apply any other topical products to the face or eye area until the study visit has been completed. If a subject arrives having not removed all makeup, subject will be required to remove the residual makeup at the clinic and wait at least 30 minutes prior to procedures.

Subjects who are wearing a face mask should continue to do so until seated in an exam room, in accordance with your local guidelines. Mask removal is required for the investigator to perform the study assessments.

Photographed subjects will also be asked to remove all jewelry, eyewear and pull hair back from their face, prior to study imaging.

### 5.4.5 Packaging and Labelling

Study medication will be individually labeled (bottle pumps for trifarotene/vehicle) and assembled into kits, for subject assignment. Product appearance, packaging and labeling will ensure subject and clinical site blinding.

Each subject will have approximately 7 dispensing packs per kit, each pack containing 2 pumps to dispense according to the schedule of assessments (Baseline, Week 4, Week 8, Week 12, Week 16, Week 20 and Extra). However only 1 bottle will be dispensed at each dispensing interval. The extra bottle is in case the subject loses or runs out of IP. Subjects should be instructed to apply the IP daily to their face for 24 weeks.

### 5.4.6 Study Drug Management

### 5.4.6.1 Storage of Study Drugs

Study drugs must be stored in a safe and secure area with restricted access, upon receipt and throughout the study. Refer to storage conditions as specified in Section 5.4.1 – Study Drug Description.

GALDERMA R&D RD.06.SPR.204245 V00 18AUG2021 Page 43 of 104

Storage should be temperature monitored daily, and if a temperature excursion occurs, the designated personnel should promptly inform the study monitor, as specified in the current version of the pharmacy manual.

## 5.4.6.2 Study Drug Accountability

Upon receipt of the study drugs, the site must conduct a complete inventory of all study drugs. If a damaged shipment is received and/or a temperature excursion has been experienced, the site will notify the Sponsor/CRO and follow the guidelines according to the current version of the pharmacy manual.

All study drugs sent to the Investigator/Institution will be accounted for and no unauthorized use is permitted. Subjects will be instructed to return all study drugs and dosing calendar per the Schedule of Assessments (Section 5.1.1.2) to review usage and dosing compliance. Subjects will be counseled on the importance of following study drugs dosing instructions.

The investigator or designee will maintain accurate records of supplies received, inventoried at the clinical trial site and used per subject. Used and unused study drugs will be appropriately reconciled by the monitor and returned to the Sponsor or designee for destruction as instructed by the Sponsor (Section 5.4.6.3 – Dispensing and Return of Study Drug).

### 5.4.6.3 Dispensing and Return of Study Drugs

Designated study personnel at each investigational site will be responsible for dispensing and retrieving the study drugs at the appropriate visits. They will also record the dispensing and returning information for each subject (see Section 5.1.1.2).

Each subject will receive study drug at Baseline, Week 4, Week 8, Week 12, Week 16, and Week 20 visits. Study drugs within each kit will be uniquely identified with a corresponding kit number and a bottle identifier to aid compliance assessment, per dosing interval. Upon dispensing, the affixed portion of the label will remain on the dispensing box. The tear-off portion of the label is to be removed from the dispenser and attached to the appropriate drug accounting record.

Each subject will be instructed on the importance of returning their study drugs (used and/or unused) as specified in the schedule of assessments (Section 5.1.1.2). Drug accountability and dosing compliance will be assessed by the designated site personnel. Subjects will be instructed to return the dosing calendar and all study medication at each study visit, for review by study personnel in the presence of the subject. At study visits Week 1 and Week 2, study drugs dispensed at Baseline will be re-dispensed after compliance checks are completed (see Section 5.4.6.4 – Treatment Compliance).

GALDERMA R&D RD.06.SPR.204245 V00 18AUG2021 Page 44 of 104

In the event of early termination/suspension of the clinical trial, a rapid recall of study drugs will be initiated. The Investigator or designee must immediately instruct the subjects to stop the study drugs and return all study drugs to the clinical trial center.

For subjects who do not complete the entire clinical trial, all used and unused study drugs should be returned by the subjects to the clinical trial center.

At the conclusion of the study, the used and unused study drugs will be returned to the Sponsor or designee in charge of the study drug management.

